Provides anaesthesia to the lateral femoral cutaneous nerve, which innervates the site of skin incision for surgical repair (in lateral approaches only)	Anaesthesia of only some of the nerve branches of the femoral nerve that supply the anterior hip capsule. No blockade of AON [15]. Unlikely to provide blockade of the obturator nerve.
Very low risk for direct neural damage due to remote injection points.	Prolonged onset due to distant injection point and slow spread.

PERICAPSULAR NERVE GROUP BLOCK

A preliminary audit at Lismore Base Hospital performed in May 2019, results show a trend toward reduced pain and morphine requirements n=6. The difference was not statistically significant.

ADVANTAGES	DISADVANTAGES
Utilises bony sonographic anatomy, therefore less variations in performance is expected.	Deeper site of infiltration requires higher technical skills.
Target site contains nerves branches that innervate the anterior hip capsule with greater frequency than FNB or FICB. Only technique that blocks the AON [15, 23]. Closer proximity to obturator nerve branches than other techniques [15]. Makes obturator blockade very likely..	Sonographic anatomy not familiar to emergency physicians. Requires re-training and experience in ultrasound guided needle techniques.
Targets small, distal purely sensory nerves [15, 23]. This should convey a faster onset and more complete blockade. Rapid onset is particularly valuable in the emergency department, where the patient is likely to be moved soon after the block is inserted.	Not well established clinical practice. Quality evidence not yet produced.
Infiltration site is distant from major vasculature, so LAST is less likely. It is distant to any motor nerves which eliminates the risk for major motor nerve damage.	

Aims and Objectives

1. To confirm that the PENGGB is a safe and effective intervention for analgesia of patients presenting to the emergency department with hip fractures.
2. To perform a prospective observational study to assess the PENGGB comparing analgesic efficacy vs current practice of FICB and FNB

Null hypothesis

The PENGGB provides comparable analgesia to patients with fractured neck of femur compared to the FNB and FICB.

Study Design

A prospective observational study.

Current Practice:

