1. SPIED Study Emergency Department Data Form [Appendix 4]
 - a. Emergency Department staff may choose to use this form in place of Medical Surveys should they prefer, or if there are logistical challenges encountered with Medical Surveys
2. Limb Observation Chart: [Appendix 6]
 - a. It is standard practice on the surgical ward for nursing staff to complete limb observations every 1-2 hours on patients with #NOF and record these on a limb observation chart.
 - b. This chart has been modified for the SPIED study to also record pain scores
 - c. Also includes pain score calculators for the VAS and PAINAD
3. Subjective Observed Patient Comfort During Nursing Cares [Appendix 7]

Primary outcome = reduction of pain score

VAS pain scores will be recorded at rest and on movement. Movement is defined as attempted hip flexion to 15 degrees. PAINAD scores will be single measure based on nursing observation.

This score will be documented at the following times:

- Prior to placement of nerve block in the emergency department
- 15, 30, 60 minutes post placement of block
- With routine limb observations on the surgical inpatient ward, approximately hourly

Data will be collected for 12 hours post nerve block (or the next documented score after 12 hours) or until the patient is moved to the operating room, whichever is sooner.

Sample size and statistical power

The rationale for sample size calculations:

- A reduction in visual analogue pain score of 13 mm (1.3/10) was established as being clinically significant by Todd et al in 1996 [26].
- A clinically significant difference between two treatments that reduce pain scores by 1.3/10 has not been well defined
- Cooper et al used 1.5/10 difference in pain scores as a definition of clinically significant difference between blocks [27].
- Newman et al found a standard deviation in pain score reduction of 2.4 in patients receiving regional analgesia for #NOF in 2013 [28]. This figure was used by Cooper et al for their power calculation in 2018.
- Cooper et al found standard deviations of 2.2 and 2.4 respectively for the FNB and FICB [27].
- A retrospective study of patients that received regional anaesthesia for # NOF at LBH in the first 4 months of 2019 was performed by co-investigators of this study. This data included 40 patients that received regional anaesthesia in ED, 6 of whom received a PENG block. Pain score documentation was not sufficiently reliable to inform power calculations for this observational study.

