Minimum Sample Size Calculation: Application of Student's t-Test.

Calculation assisted by using the Simple Sample Size Calculator (Android application). [Appendix 2]

- One-sided test to assess for non-inferiority
- Two sample
- Error 0.05
- Sample allocation ratio of 1:2
- Standard Deviation = 2.4
- $\mu_0 = 4$, $\mu_1 = 2.5$ (difference in pain score reduction of 1.5)
- Target (Actual) Power = 0.8000
- **Sample size = 74 (25+49)**

Duration of Data Collection

At our institution, we had 203 patients present with fractured neck of femur in 2018 and in the first 6 months of 2019 we have had 79. This is an average of 15.67 per month. Presuming this average continues and we achieve an enrolment rate of 80% and a PENG block delivered to one-third of these patients, we could expect to enrol sufficient patients in 6 months. To ensure significant power is achieved, we plan to enrol patients for a minimum of 6 and a maximum of 8 months.

Enrolment may be terminated early if we achieve a minimum enrolment of 125 patients and 41 PENG blocks. These numbers would allow for assessment of superiority (two-sided test) sensitive to a difference in pain score reduction of 1.3/10. [Appendix 3]

Secondary Outcomes

In an attempt to measure patient important outcomes, we will collect data on:

- Onset Time for analgesia (defined as the time until the first pain recorded pain score that is $\geq 1.5 / 10$ less than the pre-block pain score.
- Subjective observed patient comfort during nursing cares
- Patient preference where crossover occurs.
- Rates of block failure
- Block duration of analgesia

Subjective observed patient comfort during nursing cares:

Nursing staff caring for patients will be asked to comment on the patient's pain during standard nursing cares that require movement. These may include:

- Transfer to or from a bed
- Transfer on and off a bedpan
- Change of bedding or pad
- Other

At the time of nursing care, nurses are asked to rate the patient's analgesia as adequate or inadequate

Patient Preference where crossover occurs

- Some patients will have a repeat nerve block in the preoperative phase
- Of this population, some will receive a nerve block that is different to the block they received in ED. Hence they will have received cross over treatment and can act as their own control to compare two blocks.
- Investigators will identify these patients and they will be asked which block they found to provide more comfort.

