- Treatment in this phase of the patient's journey will be decided by the acute pain service or duty anaesthetist. The investigators will have no influence over which repeat block the patient receives.

Block failure

- Defined as maximum pain score improvement of less than 1.5 out of 10.

Duration of analgesia from nerve block

- End of block effect defined as an increase in pain score to ≤ 1.0 from pre-block pain score in a patient who had a reduction in pain score of > 1.5 at any time.

Opioid Requirement

- Opioid intake will be measured by analysis of the electronic medication chart from the insertion of block until 12 hours have passed, or the patient is checked in to the operating theatre, whichever occurs first.
- This information will be converted to milligrams of oral morphine using the Faculty of Pain Medicine Opioid Calculator

Adverse events

In an effort to detect the incidence of adverse events, the investigators will:

- Perform a keyword search of the “Continuous Doc” feature of the electronic record, after the patient is discharged from the hospital.
 - Keywords:
 - Delirium
 - Sedation
 - Constipation / Constipated
 - Aspiration
 - Naloxone
- Review the electronic medication chart for use of:
 - Naloxone
 - Antibiotics

Surgery Waiting Time:

Time to surgery will be defined as the time from Triage in the Emergency Department to the time of Check In at Operating Theatre for operative fixation.

Data collection on our cohort for the purposes of the primary outcome will cease at the time of check in to the operating theatre or at 12 hours after the insertion of nerve block, whichever is sooner.

Mean, median and longest wait times will be recorded. This information will inform future practice at our hospital.

Data Collection and Storage

Primary Data Recording Methods:

Were discussed above and are summarised here:

- ❑ Documentation in the electronic medical record record (PowerChart / FirstNet / SurgiNet) as is usual practice for all patients treated in the emergency department and those admitted to the hospital
- ❑ Documentation on the paper SPIED Limb Observation Chart [Appendix 6] which is usual practice for patients admitted to the inpatient orthopaedic and surgical ward with fractured neck of femur. The standard chart has been modified for the SPIED study to include pain scores and pain score calculators.

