- ❑ Documentation on a paper form SPIED ED Data Form [Appendix 4] in the emergency department. This is additional to usual documentation and may be replaced by utilising Medical Surveys for data entry in the ED.
- ❑ Subjective Observed Patient Comfort During Nursing Score. May be completed in paper form [Appendix 7] or within Medical Surveys.

Data Governance

Data Storage:

The completed SPIED ED Data Form [Appendix 4] will be filed by clinicians in a folder within the Acute clinical area of the Emergency Department at Lismore Base Hospital. The SPIED ED Data Form will be the enrolment record.. Completed forms will be frequently collected by the investigators and stored securely with the ED Support Offices, which require swipe card access. This data will be stored for 5 years after the completion of data collection and then destroyed.

All other paper forms associated with the SPIED Study will form part of the patient's hospital record and will be treated accordingly.

Data Access:

- Investigators who are clinicians at Lismore Base Hospital have access to the patient's electronic medical records in the usual fashion as they would for day to day clinical work.
 - Investigators who access a patient's file for the purpose of data collection rather than clinical care, will create an electronic entry to document that they are accessing the file for the purposes of the SPIED study.
- In the event that any research funding is obtained, a research assistant may have access to Medical Surveys data and eMR as do the investigators.

Statistical Analysis

Primary Outcome:

Reduction in pain scores over the first 12 hours after nerve block. We will apply the following statistical tests:

- Student's t-test to compare the reduction in pain score of patients who receive a PENGGB compared to FNB and FICB
 - Subgroup analyses of the cognitively impaired and non-cognitively impaired population. These populations will have pain scored by the PAINAD and VAS respectively.
 - Subgroup analysis of FNB and FICB separately

Secondary Outcomes

- Onset of block. Defined as the time until the first pain score ≥ 1.5 less than the pre-block pain score.
 - T-test
- Subjective observed patient comfort during nursing cares
 - Chi Square test
- Patient Preference in the event of crossover
 - Chi Square test
- Rates of block failure. Defined as not achieving a reduction in pain score of $\geq 1.5 / 10$
 - Chi square test

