- Duration of analgesia. End of block effect defined as an increase in pain on movement score to ≤ 1.0 from pre-block pain score for that patient, in a patient who had a reduction in pain score on movement > 1.5 at any time.
 - T-test

Ethical Considerations

There are several ethical considerations in the design and implementation of this study. Throughout the study design process, the authors have consulted with key members of staff within our health service:

- ❑ *Director of Research: [name]*
- ❑ *Orthopaedic Clinical Nurse Specialist: [name]*
- ❑ *Acute Pain Service Clinical Nurse Consultant: [name]*
- ❑ *Surgical Clinical Nurse Educator: [name]*
- ❑ *Geriatric Medicine CMO: [name]*
- ❑ *Department of Anaesthesia Orthopaedic Special Interest Group: [name]*
- ❑ *Department of Anaesthesia research interest group: [name], [name]*
- ❑ *Pain Specialist: [name]*
- ❑ *LBH Nursing Infection Control: [name]*
- ❑ *Rural Research Education Manager: [name]*
- ❑ *Department of Emergency Medicine: Consultant group*
- ❑ *Emergency Department Clinical Nurse Educator: [name]*
- ❑ *Emergency Department Nurse Unit Managers: [name], [name]*
- ❑ *Director of Emergency Medicine Training: [name]*
- ❑ *NOF pathway working group headed by [name]*

Research merit and integrity

Merits of this research:

- We believe the PENGGB to have a superior anatomic basis for efficacy compared to other nerve blocks for neck of femur fractures. Early experience utilising the PENG block is promising.
- Early adoption of the PENGGB which, to our knowledge, has not been studied outside of Toronto, nor within an Emergency Department would place our institution in a leading position in the emergency management of # NOF.
- The generation of evidence supporting this therapy's safety and efficacy would be expected to increase its uptake both within our institution and at other institutions. A positive study would be expected to encourage further investigation in the form of a randomised clinical trial
- Generation of evidence that the PENGGB is inferior to the standard of care would appropriately discourage clinicians from changing their practice.

Integrity:

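### Duration of analgesia is compared between blocks only in patients whose block worked, so when failure rates differ the test can understate, exaggerate or reverse a difference in analgesic time

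*Protocol*

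**What the plan says.** The second aim in the protocol is "To perform a prospective observational study to assess the PENGGB comparing analgesic efficacy vs current practice of FICB and FNB". Duration of analgesia is one of the secondary outcomes that serve it.

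- **Secondary Outcomes, Duration of analgesia from nerve block:** the end of effect is defined "in a patient who had a reduction in pain score of > 1.5 at any time".
- **Statistical Analysis, Secondary Outcomes:** "End of block effect defined as an increase in pain on movement score to ≤ 1.0 from pre-block pain score for that patient", again limited to the case "in a patient who had a reduction in pain score on movement > 1.5 at any time". The test named is a t-test.
- **Secondary Outcomes, Block failure:** "Defined as maximum pain score improvement of less than 1.5 out of 10". The analysis section lists it as "Rates of block failure. Defined as not achieving a reduction in pain score of" at least 1.5 out of 10, with a chi-square test.

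The patients who have a duration are therefore almost exactly those whose block did not fail. No section gives a failed block a duration, whether zero or any other value. Pain scores are collected until about 12 hours after the block or until the move to theatre, whichever is sooner.

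**The concern.** Whether a patient enters the duration comparison is decided after the block, by how well the block worked. If one block fails more often, it is represented only by its successes, while the other block keeps more of its patients. The t-test then answers how long a block lasts once it has worked. It does not answer how much analgesic time a patient given each block can expect, which is closer to the second aim.

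The protocol's introduction says that no data have been published on how long PENG analgesia lasts, so readers are likely to look at this result. Without a label saying that it is conditional on success, a difference in responders, or the lack of one, may be read as a property of the blocks as given. A survival method applied to the same responders would handle the cut-off at 12 h or theatre but would leave this selection in place.

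**Working it through.** **1. The plan's own figure.** Inputs from Sample size and statistical power: a "difference in pain score reduction of 1.5" (means 4 and 2.5), SD 2.4, one-sided 0.05, power 0.80, allocation 1:2.

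Smaller group = (1 + 1/2) × [(1.645 + 0.842) × 2.4 / 1.5]² ≈ 23.7, rounded up to 24. The larger group is 48, total 72. The protocol states 74 (25+49), where the exact t-test power is 0.809. The figure reproduces and is not in dispute. The protocol gives no expected failure rate and no expected duration.

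**2. Share excluded, if the sizing figures described peak reductions.** Assume normal peak reductions. Call the block with mean 4 block A and the block with mean 2.5 block B. The protocol does not say which would be PENG.

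- Block A: Φ((1.5 − 4)/2.4) = 0.149
- Block B: Φ((1.5 − 2.5)/2.4) = 0.338

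Of 25 and 49 patients, 25 × 0.851 ≈ 21 and 49 × 0.662 ≈ 32 remain.

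**3. How far that share depends on the reading.** Selection is on a reduction at any time, so on the best of repeated scores. Suppose instead that 2.4 is the SD of a reduction at one time, with a within-patient SD of 1.0 (an assumption). The excluded shares are then about 5% and 17% with five post-block scores, and about 3% and 11% with fourteen.

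**4. Effect on the comparison.** With the shares from step 2 and failed blocks counted as 0 h:

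all-patient difference (A − B) = 0.851 × (mean in A responders) − 0.662 × (mean in B responders).

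The responder means below are assumptions.

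| Responder means A, B (h) | Responders only, A − B (h) | All patients, A − B (h) |
|---|---|---|
| 8, 8 | 0 | +1.52 |
| 8, 7 | +1.0 | +2.18 |
| 8, 6 | +2.0 | +2.84 |
| 7, 8 | −1.0 | +0.67 |
| 6, 8 | −2.0 | −0.19 |

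Rows 2 and 3: the advantage of the block that fails less is understated. Row 4: the sign reverses. Row 5: the advantage of the block that fails more is exaggerated. The all-patient difference is zero when B responders last 0.851/0.662 ≈ 1.29 times as long as A responders.

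**5. If duration follows the size of the relief.** Assume relief wears off linearly from its peak until the score is within 1.0 of the pre-block score, capped at 12 h, at 0.3, 0.5 or 0.8 points per hour (assumed rates). By simulation the responder-only differences are about 1.3, 1.5 and 1.0 h, against about 2.7, 2.3 and 1.5 h in all patients. Here the direction is understatement, because one block is simply better throughout.

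**The case against.** The strongest reply is that the protocol splits efficacy into two parts: how often a block works and how long it lasts when it works. Failure has its own chi-square test, so nothing is concealed. Duration given success is a coherent quantity and a reasonable answer to the gap the introduction names. This stands as a case for reporting the responder-only duration. It does not make the t-test a comparison of the blocks as given, because the two groups of responders are selected to different degrees when failure rates differ. Nor does the protocol label the duration as conditional on success or ask that it be read with the failure rate.

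Three further replies also stand:

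- Row 1 of the table is not evidence of bias. If responders last equally long, 0 h is the right answer to the conditional question, and 1.52 h is 8 × (0.338 − 0.149) with unrounded shares: the failure-rate difference expressed in hours.
- The means 4 and 2.5 are sizing inputs, of which only the difference matters. They do not forecast failure. If the blocks fail equally often, there is no differential selection.
- Duration is one of several secondary outcomes in a non-randomised study, with no sample size calculation of its own.

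A reader might infer that the design always understates a real difference, or that it hides failed blocks. The documents support neither: the direction depends on how long responders to each block last, which the protocol does not give, and failure is tested openly.

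**Conclusion.** The point holds in a limited form. Duration is tested between blocks in a set selected on a post-block outcome, and with unequal failure rates that test can understate, exaggerate or reverse the difference in analgesic time. The separate failure test discloses the failures but does not correct the duration comparison.

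The size cannot be fixed from the protocol. The exclusion of about 15% and 34% assumes normal peak reductions with the sizing means and SD. Under the single-time reading it falls to between about 3% and 5% in one group and between about 11% and 17% in the other, given the assumed within-patient SD. Every figure in hours rests on assumed durations or wear-off rates. The primary outcome and the sample size are unaffected. This is a cheap improvement to a secondary analysis, not a flaw in the main result.

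**What to change.** Change the duration wording in both places, Secondary Outcomes and Statistical Analysis:

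- Base the between-block comparison on all blocked patients with a pre-block score. Count 0 h for those with post-block scores who never reach the response threshold. Treat a patient with no post-block score as missing, not as 0 h.
- Use a method that handles durations cut off at 12 h or at theatre, for example a difference in restricted mean analgesic time up to 12 h, in place of the t-test.
- Report the responder-only duration descriptively, labelled as among successful blocks, beside the failure rate and with no between-block claim.
- Make the two definitions agree so that the all-patient set can be formed. One requires a movement score and the other does not, and patients scored by PAINAD have a single score. A reduction of exactly 1.5 is at present neither a failure nor in the duration set.

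The cost is wording only; no new data are needed. The downside is that the all-patient figure mixes failure with wear-off, so both figures must be shown.

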Short et al describes a quantifiable anatomical explanation for incomplete or failed anaesthesia from FNB or FICB in patients with #NOF. Several studies demonstrate that the FN block and FICB do not reliably block the obturator nerve or the lumbar plexus [16-22]. Distally, the high articular branches of the FN and AON are consistently located between the anterior inferior iliac spine and the iliopubic eminence [15]. The articular branches of the ON are located close to the inferomedial acetabulum. [15,23]. Subsequently the pericapsular nerve group block (PENGB) was designed to target the articular branches of the FN and AON by infiltrating the sub-psoas space at the level of the iliopubic eminence [23]. A case series of 5 consecutive patients with #NOF at Toronto Western Hospital was published in November 2018 and demonstrated the feasibility and efficacy of this block [23]. There is no published data describing the duration of analgesia provided by the PENG block.

The PENGB has subsequently been adopted by several practitioners at Lismore Base Hospital for the treatment of #NOF. We believe there is a study ongoing in peri-operative patients comparing PENGB to FICB in Toronto. We are not aware of any research into the utilisation of the PENGB in the emergency department setting. Searches of multiple study registries reveal no ongoing trials.

A retrospective study of patients that received regional anaesthesia for # NOF at LBH in the first 4 months of 2019 was performed. This data included 40 patients that received regional anaesthesia in ED, 6 of whom received a PENG block.

In this audit, patients' total opioid requirements from time of block to time of operation were recorded and converted to oral morphine equivalents using the ANZCA Faculty of Pain Opioid Calculator.

This audit found that patients receiving PENG blocks required fewer opioids pre operatively (mean = 22.67 mg) than did patients who did not receive a PENG block (FIB mean = 26.15 mg and FNB mean = 30.90 mg). Of note, patients receiving PENG blocks required fewer opioids in the 0-6 hours period immediately post block (mean = 3.00 mg) than did patients who did not receive a PENG block (FIB mean = 6.38 mg and FNB mean = 9.10). These results were not statistically significant ($p = 0.5$). The null hypothesis was retained. One adverse event relating to PENG blocks was documented in the records (failed block).

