Confirmation of the efficacy and safety of the PENGGB would be expected to lead to increased adoption of the technique in Emergency Departments around Australia. Should the PENGGB prove to be inferior to the present standard of care then this would also be valuable information to guide practitioners to continue to use the ultrasound-guided femoral nerve block to treat hip fractures in the emergency department. Probably, this study will confirm that the PENGGB is efficacious and safe without the statistical power to prove superiority to the existing standard of care. This will inform further research on the topic.

There recently is a significant research effort in Australia being directed to comparing the ultrasound-guided femoral nerve block to the ultrasound-guided FICB. There remains equipoise on this matter despite a randomised controlled double-blind trial of 100 patients published in 2018 [27]. There is also research in progress comparing the FICB as a single shot block versus a repeated or continuous infusion via a catheter inserted in the ED. If the PENGGB is the superior intervention, then these impressive research efforts might be better redirected to investigating the PENGGB.

Dissemination of results:

The principal investigator intends to disseminate the results of this study by:

- publication in a peer-reviewed journal approved by the college of emergency medicine and/or
- presenting results at the Australasian College of Emergency Medicine Annual Scientific meeting or Winter Symposium.

It is likely that co-investigators will disseminate the results of this study by presenting at relevant scientific meetings for Anaesthesia.

Appendices:

1. FirstNet NOF order set
2. Power Calculation Minimum
3. Power Calculation Maximum
4. SPIED ED Data Form
5. SPIED Enrolment Checklist
6. SPIED Limb Observation Chart
7. Subjective Observed Comfort During Nursing Care
8. nil
9. Inclusion-Exclusion Criteria
10. nil
11. SPIED Folder Contents
12. Patient Information and Consent

REFERENCES

1. Dyer, S.M., et al., *A critical review of the long-term disability outcomes following hip fracture*. BMC Geriatr, 2016. 16: p. 158.
2. Lystad, R.P., C.M. Cameron, and R.J. Mitchell, *Mortality risk among older Australians hospitalised with hip fracture: a population-based matched cohort study*. Arch Osteoporos, 2017. 12(1): p. 67.
3. ~~Dyer, S.M., et al., *A critical review of the long-term disability outcomes following hip fracture*. BMC Geriatr, 2016. 16: p. 158.~~

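### Aim 1 is to confirm that the PENG block is safe, but 25 to 41 blocks with no case of a given harm would still leave a rate of 7% to 11% possible (one-sided 95% limit)

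*Protocol*

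**What the plan says.** Aims and Objectives, item 1, reads "To confirm that the PENGGB is a safe and effective intervention for analgesia of patients presenting to the emergency department with hip fractures". It carries no qualification.

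Outcomes and Significance returns to the claim with a hedge: "Probably, this study will confirm that the PENGGB is efficacious and safe without the statistical power to prove superiority to the existing standard of care". The same section expects confirmed efficacy and safety to increase use of the technique in Australian emergency departments. The only power limitation it acknowledges concerns superiority.

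The sample sizes come from pain-score reduction alone. The minimum is "Sample size = 74 (25+49)", described as "One-sided test to assess for non-inferiority" with "Target (Actual) Power = 0.8000". Duration of Data Collection adds: "Enrolment may be terminated early if we achieve a minimum enrolment of 125 patients and 41 PENG blocks". That second threshold is tied to a two-sided pain-score comparison sensitive to 1.3 out of 10.

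Adverse events are to be found after discharge, by a keyword search of the record and a review of the medication chart. The protocol gives no acceptable event rate, safety hypothesis or precision target. The Risk section names local anaesthetic systemic toxicity as the most serious adverse event of regional anaesthesia and gives no rate for it.

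**The concern.** To confirm safety, a study must be able to rule out harm above some stated rate. The protocol states no such rate, and the number of PENG blocks was chosen for a different question. A small group with few or no events is compatible both with a very safe block and with one that causes an uncommon serious harm.

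The conclusion at stake is one the protocol links to changes in practice. If Aim 1 stands as worded, a low event count would appear to meet it, although the data could not distinguish between those two situations. An analysis plan cannot repair this, because the limit lies in the number of blocks and the aim is protocol content.

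**Working it through.** **Inputs from the protocol.** PENG blocks: 25 (minimum sample size) and 41 (early-termination threshold). SD 2.4; difference 1.5 (one-sided) or 1.3 (two-sided); error 0.05; power 0.80; allocation 1:2. Accrual: 203 patients in 12 months plus 79 in 6 months, 80% enrolled, one-third given PENG, for 6 to 8 months.

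**1. Reproducing the plan's sample sizes.** With 1:2 allocation, the normal approximation for the PENG group is n = 1.5 × [SD × (z_α + z_power) / difference]².

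- Minimum: 1.5 × [2.4 × (1.645 + 0.842) / 1.5]² = 23.7, so 24 + 48 = 72. Exact t-test power is 0.797 at 24 + 48 and 0.809 at 25 + 49. The stated 74 is reproduced.
- Early termination: 1.5 × [2.4 × (1.960 + 0.842) / 1.3]² = 40.1, so 41. Exact t-test power at 41 + 84 is 0.805. The stated 125 and 41 are reproduced.

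Both calculations are right for pain scores. Neither has a safety input.

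**2. PENG blocks expected from the stated accrual.** (203 + 79) / 18 = 15.67 per month.

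- 6 months: 15.67 × 6 × 0.8 / 3 = 25.1
- 8 months: 15.67 × 8 × 0.8 / 3 = 33.4

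So 25 to 41 is a fair range. Its upper end is above what the stated accrual yields in the maximum enrolment period.

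**3. What zero observed cases would exclude.** For a harm with no cases in n blocks, the exact binomial upper limit is 1 − 0.05^(1/n) (one-sided 95%) or 1 − 0.025^(1/n) (two-sided 95%).

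| PENG blocks | One-sided 95% | Two-sided 95% |
|---|---|---|
| 25 | 11.3% | 13.7% |
| 33 | 8.7% | 10.6% |
| 41 | 7.0% | 8.6% |

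The 3/n rule of thumb agrees with the one-sided column: 12.0% for 25 and 7.3% for 41.

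If one case is seen, the two-sided 95% upper limit is 20.4% for 25 blocks and 12.9% for 41.

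**4. Chance of seeing no case at assumed true rates.** The protocol gives no rate, so 1% and 5% are illustrations. The probability is (1 − p)^n.

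- p = 1%: 0.99^25 = 78%; 0.99^41 = 66%
- p = 5%: 0.95^25 = 28%; 0.95^41 = 12%

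**5. Blocks needed, with no cases, to exclude a given rate** (one-sided 95%). n = ln 0.05 / ln(1 − p), rounded up: 59 for 5%, 149 for 2% and 299 for 1%. These rates are also illustrations.

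**The case against.** The best reply is that this is only wording. The sentence in Outcomes and Significance begins with a hedge, is followed by a remark that the result will inform further research, and is neither an analysis rule nor a decision criterion. Research merit and integrity expects a positive study to encourage a randomised trial, and the protocol commits to publishing positive or negative results. All of this is true, and it softens the forecast. It does not reach Aim 1, which has no hedge, or the expectation that confirmed safety will widen adoption.

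A second reply is that zero events is not the likely result for everything collected. Delirium and constipation are among the search terms, and the protocol describes a frail population at risk of delirium and opioid harm. This also stands: the zero-event limits apply to a block-related harm that happens not to be seen. They are not a forecast for all adverse events together.

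Several stronger readings are tempting and are not supported:

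- **That PENG already looks unsafe.** The audit states "One adverse event relating to PENG blocks was documented in the records (failed block)". A failed block is an analgesic failure, and the protocol measures block failure as a separate pain outcome. It says nothing about harm.
- **That serious harms would probably go unseen.** A harm is more likely missed than seen only if its true rate is below about 2.7% with 25 blocks (1 − 0.5^(1/25)) or 1.7% with 41 (1 − 0.5^(1/41)). The protocol gives no rate to compare with these.
- **That the lack of a named test for adverse events is a defect.** A statistical analysis plan may supply one. Surgery waiting time is also given only descriptive summaries.
- **That the protocol would treat zero events as proof.** It states no such rule.

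**Conclusion.** The point holds as a mismatch between a stated aim and what the design can show. With 25, about 33 or 41 PENG blocks and no observed case of a given harm, rates up to 11.3%, 8.7% or 7.0% remain compatible with the data (one-sided 95%). Uncommon serious harms, including the one the protocol itself ranks as most serious, cannot be excluded at these numbers. With no rate defined as safe, there is also no criterion by which safety could be confirmed.

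The limits assume independent patients, a common event rate and complete detection of cases. The last assumption is favourable to the study, because the listed keywords do not name systemic toxicity. The value 41 is a minimum for optional early termination, not a ceiling on enrolment; a larger PENG group would lower the limit in proportion, roughly as 3/n.

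The primary pain analysis and its sample size are unaffected. The figures show imprecision about harm and are no evidence of harm.

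**What to change.** Reword Aim 1 so that its safety part is to estimate the incidence of adverse events by block type (PENG, FNB, FICB), with exact 95% confidence intervals.

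In Outcomes and Significance, replace the forecast of confirmed safety with the upper limit that the study can exclude if no case of a given harm is seen: about 11% with 25 PENG blocks, 9% with 33 and 7% with 41, labelled as one-sided 95%. Add that an absence of events will not be reported as confirmation of safety. Adjust the adoption sentence in the same section to match.

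The cost is a change to one aim and one paragraph, plus a descriptive table of event rates by block. No extra patients or data collection are needed. The downside is a less favourable stated claim.
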